8.3 Variables

The sections below include outcomes, treatment exposure and PPE use, COVID-19 exposure, COVID-19 vaccinations, and other variables to be measured and accounted for in the study analyses. Refer to [Appendix 2](#) for further details.

8.3.1 *Clinical Outcomes Variables*

- WHO Ordinal Scale for Clinical Improvement of COVID-19 (adapted, abbreviated version)
 - SARS-CoV-2 (uninfected/infected)
 - Ambulatory status (limitation/no limitation of activities)
 - Hospitalized with no intensive care unit (ICU) or mechanical ventilation (mild)
 - Hospitalized with ICU and/or mechanical ventilation (severe)
 - Death

8.3.2 *Prophylactic Treatment (Treatment Exposure)*

- Types, intake frequency, and doses of prophylactic treatments
 - Treatment name
 - Date started
 - Date stopped
 - Dose (intake)
 - Duration of treatment
 - Dose frequency and dosing interval
 - Status (stopped/ongoing)
 - Reason for stopping (not available/side effects/expense/other)
 - Number of missed doses and reason (not available/side effects/expense/other)

8.3.3 *History of Exposure to COVID-19 Patients*

- At enrollment
 - Self-reported ongoing and recurrent exposure (yes/no)
 - WHO exposure definition (3 questions) (yes/no)
 - Direct patient care (yes/no)
 - Face-to-face contact (yes/no)
 - Present during aerosol-generating procedure (yes/no)
- Weekly follow-up
 - Self-reported ongoing and recurrent exposure (yes/no)
 - WHO exposure definition (3 questions) for past week

- Days worked past week
- Number of COVID-19 cases exposed to in the past week

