Pneumonia	X	X	-
Nausea or vomiting	X	X	-
Headache or migraine	X	X	-
Abdominal pain (pain in tummy)	X	X	-
Asthenia (weakness or loss of strength)	X	X	-
Arthralgia (joint pain)	X	X	-
Anosmia (loss of smell)	X	X	-
Ageusia (loss of taste)	X	X	-
Blue coloring in toes	X	X	-
Diarrhea (two or more looser-than-normal stools in 24 hours)	X	X	-
SARS-CoV-2 testing			
Tested? (yes/no)	X	X	-
Type of test	X	X	-
PCR (positive/negative)	X	X	-
Antigen test (positive/negative)	X	X	-
Serology (IgG and/ or IgM, positive/negative or titer)	X	X	-
Date of test	X	X	-
Serology testing	X	X	-
Household history (COVID-19)			
Number of household contacts	X	X	-
Additional household member(s) exposed to COVID-19 (yes/no) If yes, how many?	X	X	-
Additional household member(s) with symptoms consistent with COVID-19 (yes/no) If yes, how many?	X	X	-
Additional household member(s) diagnosed with COVID-19 (yes/no) If yes, how many?	X	X	-
Underlying conditions and key morbidities			
Chronic lung disease	X	-	-
Diabetes mellitus	X	-	-
Cardiovascular (heart) disease	X	-	-
Chronic renal (kidney) disease	X	-	-
Chronic liver disease	X	-	-
Immunocompromised condition (HIV/AIDS, organ transplant, other)	X	-	-
Tuberculosis	X	-	-
Neurologic/neurodevelopmental	X	-	-
Hypertension (high blood pressure)	X	-	-
History of stroke	X	-	-
Other chronic diseases	X	-	-
If female, currently pregnant	X	-	-
If female, currently breastfeeding/lactating	X	-	-
Job characteristics			
Type of healthcare work	X	-	-

Primary work location (ED, ICU, Medical floor)	X	X	-
Number of hours with patients	X	X	-
Concomitant medications (other than for COVID-19)			
Antibiotics (yes/no)	X	X	-
Antimalarials (yes/no)	X	X	-
Antiparasitics (yes/no)	X	X	-
Antiretrovirals for HIV (yes/no)	X	X	-
Antivirals (yes/no)	X	X	-
Medication for high blood pressure and cardiovascular disease (yes/no)	X	X	-
Nonsteroidal Anti-inflammatory Drugs (NSAIDs) (yes/no)	X	X	-
Botanicals (yes/no)	X	X	-
Immunocompromising drugs (yes/no)	X	X	-
COVID-19 vaccine (to be selected as applicable)			
Convidicea (Ad5-nCoV)	X	X	
CoronaVac (Sinovac)	X	X	
Covaxin (BBV152)	X	X	
EpiVacCorona (Vector Institute)	X	X	
Janssen Pharmaceuticals (Johnson & Johnson) (Ad26.COV2.S)	X	X	
Moderna COVID-19 Vaccine	X	X	
Novavax (NVX-CoV2373)	X	X	
Oxford-AstraZeneca COVID-19 Vaccine	X	X	
Pfizer-BioNTech COVID-19 Vaccine	X	X	
Sinopharm BBIBP-CorV	X	X	
Sputnik V COVID-19 Vaccine	X	X	
Other (please specify)	X	X	

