6.1 Overview.....	17
6.2 Missing values.....	18
6.2.1 Missing values for non-outcome variables	18
6.2.2 Missing values for outcomes.....	18
6.3 Descriptive analyses.....	18

6.3.1	Facility characteristics.....	19
6.3.2	Demographic characteristics.....	19
6.3.3	Household characteristics.....	20
6.3.4	Exposure to COVID-19 patients.....	20
6.3.5	Medical history.....	21
6.3.6	Medications for non-COVID-19 related purposes.....	22
6.3.7	Prophylactic medications.....	23
6.3.8	PPE usage	24
6.3.9	COVID-19 symptoms.....	25
6.4	Primary analysis	26
6.4.1	Frailty model: mixed effect Cox regression	26
	Table 5.4.1.....	26
6.5	Secondary analysis	27
6.6	Subgroup analyses	28
6.7	Sensitivity analyses	28
7	Minimization of study bias.....	30
7.1	Selection bias	30
7.2	Survival bias	30
7.3	Recall bias.....	30
7.4	Information bias.....	30
7.5	Indication bias.....	30
7.6	Protopathic bias	31
8	References	31
9	Appendix.....	32
9.1	Shell tables.....	33
	Table 8.2.1 COVID-19 exposure status among all screened healthcare workers.....	33
	Table 8.2.2 Primary and Secondary Outcomes at baseline and follow-up among the overall population	34
Table 8.2.3	Static Variables by COVID-19 indication	35
Table 8.2.4	Household characteristics at baseline by COVID-19 indication.....	37
Table 8.2.5	COVID-19 exposure at baseline by COVID-19 indication	39
Table 8.2.6	Comorbidities at baseline by COVID-19 indication.....	40

Table 8.2.7 Concomitant medications at baseline by COVID-19 indication.....	41
Table 8.2.8 Prophylaxis use.....	43
Table 8.2.9 PPE usage at baseline.....	44

1 Introduction

The purpose of this statistical analysis plan (SAP) is to provide an analytic framework for the study “International Registry of Healthcare Workers Exposed to COVID-19 Patients (UNITY Global)”. This SAP addresses the statistical analyses that will be carried out in support of the protocol objectives. This analysis plan is based on the protocol version 1.0 of the study dated 08 June 2020.

2 Objectives of the study

This is an international registry of HCWs exposed to SARS-CoV-2 while caring for confirmed or clinically diagnosed COVID-19 patients. The aim of this registry is to generate real-world evidence in HCWs to potentially inform recommendations and policies on prevention measures, including prophylactic use of potential drug therapies in HCWs.

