3.5 Study outcomes

3.5.1 Primary Outcome

- Occurrence of SARS-CoV-2 infection among HCWs caring for COVID-19 patients, in terms of time, geography, healthcare setting, and type of HCW. SARS-CoV-2 infection will be defined as a composite outcome diagnosed via the following methods:
 - By test – positive test results – confirmed diagnosis
 - Clinical diagnosis
 - By symptoms
 - Hospitalisation due to COVID-19 illness

Sensitivity analyses will be conducted using confirmed (by positive test results) diagnosis only, and diagnosis by other means, as specified above.

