3.5.2 Secondary Outcomes

For the following outcomes, infection status will be defined as per the composite primary outcome. Ambulatory status and hospitalisation will be based on responses to the relevant questions in the survey. Mortality will be based on the survey response of each subject's secondary contact. Prophylactic treatment will be based on relevant questions from healthcare worker's surveys.

- Occurrence of SARS-CoV-2 uninfected HCWs
- Occurrence of SARS-CoV-2 infection with ambulatory status and no limitation of activities. This will be defined as subjects reporting COVID-19 related symptoms, clinical diagnosis of COVID-19 or positive test results but reporting "No" limitation of activities due to their symptoms and no hospitalisation.
- Occurrence of SARS-CoV-2 infection with ambulatory status and limitation of activities. This will be defined as subjects reporting COVID-19 symptoms, clinical diagnosis of COVID-19 or positive test results and reporting "Yes" to having their usual activities limited being limited due to their symptoms, but no hospitalisation.
- Occurrence of hospitalisation due to COVID-19 illness with mild disease. This is defined as being hospitalised without being admitted to the ICU or without ventilation
- Occurrence of hospitalization due to COVID-19 illness with severe disease. This is defined as being hospitalised with either admittance to the ICU and/or receiving ventilation.
- Occurrence of all-cause mortality

- Type of prophylactic treatments (Chloroquine, Hydroxychloroquine, Azithromycin, Lopinavir/ritonavir, Ivermectin, others) by dose, frequency and duration, overall and by country/region/site. To note, prophylactic treatment use will be defined by relevant indication from 'prophylactic treatment' section of the survey; in addition, if there is an indication of drugs in 'concomitant medications' section that are also listed but not selected under 'prophylactic treatment' section, those indications will be added too.

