3.6.5 Other Covariates

- COVID-19 symptoms (and date the symptoms begin)
 - Fever (temperature over 38°C)
 - Subjective fever (felt feverish)
 - Chills
 - Myalgia (muscles hurt or ache)
 - Rhinorrhea (runny or drippy nose)
 - Pharyngitis (sore throat)
 - Cough (new onset or worsening of chronic cough)
 - Dyspnea (hard to breathe or difficulty breathing)
 - Pneumonia
 - Nausea or vomiting
 - Headache or migraine
 - Abdominal pain (pain in tummy)
 - Asthenia (weakness or loss of strength)
 - Arthralgia (joint pain)
 - Anosmia (loss of smell)

- Ageusia (loss of taste)
- Blue coloring in toes
- Diarrhea (two or more looser-than-normal stools in 24 hours)
- SARS-CoV-2 testing
 - Type of test, if known
 - PCR (positive/negative)
 - Antigen test (positive/negative)
 - Serology (IgG and/or IgM, positive/negative or titer)
 - Date of test
- Household history (COVID-19)
 - Number of household contacts
 - Additional household member(s) exposed to COVID-19 (yes/no). If yes, how many
 - Additional household member(s) with symptoms consistent with COVID-19 (yes/no). If yes, how many?
 - Additional household member(s) diagnosed with COVID-19 (yes/no). If yes, how many
- Healthcare worker-level covariates
 - Demographics at entry
 - Underlying conditions and key comorbidities
 - Job characteristics
 - Concomitant medications
 - Blood type
- Healthcare facility characteristics
 - Country, region
 - Urban or rural setting
 - Type of facility (public/private/community healthcare)
 - Teaching/university hospital or non-teaching
 - Capacity
 - number of patients tested for COVID-19
 - number of COVID-19 patients treated
 - number of hospitalized beds (overall, ICU, emergency department)
 - number of exposed HCWs
 - number of HCWs tested for COVID-19
 - Number of HCWs who developed confirmed or clinically diagnosed COVID-19
 - Number of HCWs who died from COVID-19
 - Approved PPE use policy, and experience of PPE shortage
 - Approved prophylactic treatment policy
 - Shortage of COVID-19 related tests
 - BCG vaccination policy
- Concomitant medications (other than for COVID-19)
 - Antibiotics (yes/no). If yes, please specify.

- Azithromycin
- Trimethoprim/sulphamethoxazole
- Macrolide antibiotics (roxithromycin, clarithromycin, erythromycin)
- Other antibiotics
- Antimalarials (yes/no). If yes, please specify.
 - Hydroxychloroquine
 - Chloroquine
 - Sulfadoxine-pyrimethamine (SP)
 - Other antimalarials
- Antiparasitics (yes/no). If yes, please specify.
 - Ivermectin(yes/no)

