6.3.9 COVID-19 symptoms

The distribution of COVID-19 symptoms will be displayed for the following time periods after first indication of symptoms:

- Symptoms at any time on or after first symptoms seen for the HCW
- Symptoms within 1 week after first symptoms seen for the HCW
- Symptoms within 1-2 weeks after first symptoms seen for the HCW
- Symptoms within 2-4 weeks after first symptoms seen for the HCW
- Symptoms >4 weeks after first symptoms seen for the HCW

A summary of the proportion of HCWs that had at least one symptom, at least two symptoms, at least three symptoms will also be displayed within these time periods. A histogram will be produced where the bins along the x-axis are the number of unique symptoms each HCW reports on their survey. This descriptive analysis will aid in determining which symptoms or group of symptoms will be considered for diagnosing HCWs as being COVID-19 infected.

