6.7 Sensitivity analyses

The following sensitivity analyses will be performed for the primary analysis:

- According to the four definitions of the primary outcome of COVID-19 infection (ie. positive test only, symptoms only, clinical diagnosis only, hospitalized only)
- Imputing unexplained drop-outs as events. Healthcare workers that are lost to follow-up will be treated as positive for COVID-19 infection.

In the event that the estimated hazard ratio of treated versus control in the primary analysis is 0.8 or less, but no statistical significance can be established due to a small sample size, an alternative approach such as empirical Bayesian meta-analysis will be employed to leverage published local data.

7 Minimization of study bias

As this is an observational study based on self-reported information from HCWs, there are several potential limitations and biases that will need to be considered, as follows:

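### Symptoms reported after a COVID-19 vaccine dose can count as the primary infection event, because the symptom route is still undefined and the SAP has no vaccination data and no post-dose rule

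*SAP*

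**What the plan says.** SAP 3.5.1 states that "SARS-CoV-2 infection will be defined as a composite outcome diagnosed via the following methods". The four routes are a positive test, a clinical diagnosis, symptoms, and hospitalisation for COVID-19. The symptom route has no required set, minimum count, duration or exclusion for another cause.

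SAP 3.5.2, repeated in 6.5, shows how symptoms enter the ambulatory outcomes: "This will be defined as subjects reporting COVID-19 related symptoms, clinical diagnosis of COVID-19 or positive test results". Reported symptoms are enough without a test or diagnosis. The source is the 18-item list in SAP 3.6.5, "COVID-19 symptoms (and date the symptoms begin"), which includes measured and subjective fever, chills, myalgia, headache, asthenia, arthralgia and nausea. Protocol Appendix 2 records whether symptoms developed and when, but not their suspected cause.

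The qualifying symptoms are not settled. SAP 6.3.9 says of its symptom tabulations: "This descriptive analysis will aid in determining which symptoms or group of symptoms will be considered for diagnosing HCWs as being COVID-19 infected".

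Protocol v1.1 added "COVID-19 vaccine (to be selected as applicable") to Appendix 2, by product, at enrollment and weekly. Protocol 8.3 counts "COVID-19 vaccinations, and other variables to be measured and accounted for in the study analyses". The SAP's introduction says "This analysis plan is based on the protocol version 1.0 of the study dated 08 June 2020". COVID-19 vaccination is absent from the SAP's variable list, from model Table 5.4.1 and from its outcome rules.

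**The concern.** If a vaccine dose can produce fever, chills or muscle pain, a worker who reports these in the week of a dose looks the same, under the symptom route, as one with an untested infection. That vaccines do this, and how often, is an assumption here because the documents are silent on it.

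Two things are at stake:

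- **Equal vaccination in both prophylaxis groups.** False events add the same risk to each group, pull the ratio toward 1 and cost power.
- **Unequal vaccination.** False events fall more heavily on one group and can give an inert drug an apparent benefit or harm.

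The choice of symptoms in SAP 6.3.9 is itself exposed. It will be made from a distribution that may contain post-dose reports, with nothing to identify them. Errors are hard to undo later, because protocol 8.8.1 says submitted data will not be queried and 8.8.2 says there are no source documents.

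**Working it through.** **Inputs from the documents** (SAP sections 5 and 6.1): N = 10,000; 20% unexposed, so 2,000 vs 8,000; risk 10% in the unexposed; RR 0.78, so 7.8% in the exposed; two-sided 5%; stated power 80%.

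**Plan's own figure.** Expected events are 2,000 × 0.10 + 8,000 × 0.078 = 824. Reading the RR as a hazard ratio, Schoenfeld power is Φ(|ln 0.78| × √(824 × 0.2 × 0.8) − 1.96) = Φ(0.2485 × 11.48 − 1.96) = 81.4%, which reproduces the stated 80%. The pooled two-proportion formula gives 87.7%, so Schoenfeld is used below.

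**Equal vaccination.** Let f be the risk of a false event, that is, the share dosed in follow-up times the share of those whose symptoms are scored. Observed risks are 0.10 + 0.90f (unexposed) and 0.078 + 0.922f (exposed). All values of f are assumptions.

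| f | Example (dosed × scored) | Observed risks | RR | Events | Schoenfeld power |
|---|---|---|---|---|---|
| 0 | none | 10.00% vs 7.80% | 0.780 | 824 | 81% |
| 0.5% | 5% × 10% | 10.45% vs 8.26% | 0.791 | 870 | 79% |
| 1% | 10% × 10% | 10.90% vs 8.72% | 0.800 | 916 | 77% |
| 4% | 20% × 20% | 13.60% vs 11.49% | 0.845 | 1,191 | 64% |
| 12% | 30% × 40% | 20.80% vs 18.86% | 0.907 | 1,925 | 40% |

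At 1% the planned effect already sits at the limit of 0.8 that SAP 6.7 sets for its Bayesian fallback.

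**Unequal vaccination, inert drug.** Assume a true risk of 10% in both groups and 20% of those dosed scored. With 40% of unexposed and 20% of exposed workers dosed, the risks are 0.10 + 0.90 × 0.40 × 0.20 = 0.172 and 0.10 + 0.90 × 0.20 × 0.20 = 0.136. The RR is 0.136/0.172 = 0.79, about the size of the planned effect. With uptake reversed it is 0.172/0.136 = 1.26.

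**What a vaccination covariate can do.** Weekly hazards were simulated under the same assumptions.

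- For the inert drug with unequal uptake, the hazard ratio was 0.78 without a vaccine term and 1.00 with a time-varying dose-week term. With uptake reversed it went from 1.30 to 1.00.
- For a real effect with equal uptake (25% dosed, 30% scored), it was about 0.86 with or without the term.
- Excluding dose-week symptom events in that second case brought it back to 0.75. The hazard ratio implied by 10% vs 7.8% is ln(0.922)/ln(0.90) = 0.77, so this is the true effect to within simulation error.

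The term therefore removes the distortion from unequal uptake but not the attenuation. The exclusion rule deals with the attenuation.

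**The case against.** Four objections have force.

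1. **The rule is open.** A reader might infer that vaccinated workers with fever or chills will be scored as infected. The documents do not support that. SAP 6.3.9 has not chosen the symptoms, and a set that required loss of smell, for example, might admit few post-dose reports. What stands is that they can be scored, and that they would be if the wording of 3.5.2 and 6.5 were applied literally. Post-dose symptoms are also one case of a wider gap, since any other febrile illness could enter the same way.
2. **Safeguards exist.** SAP 6.7 reruns the main model once per route: "According to the four definitions of the primary outcome of COVID-19 infection (ie. positive test only, symptoms only, clinical diagnosis only, hospitalized only"). The test, diagnosis and hospitalisation versions leave out symptom-only events and would expose the problem. They do not change the primary estimate. The test-only version may also be thin, because SAP 3.1 mandates no testing and the facility survey records test shortages.
3. **The size is assumed.** Uptake during follow-up and symptom frequency are not in the documents. At 0.5% false events the loss is trivial. A reader might infer that vaccination was added because workers were being vaccinated during follow-up, but the amendment's stated reason is to have current information on available prophylaxis. The vaccine questions came with Amendment 1 in June 2021, a year after the original protocol, so the share of follow-up affected is unknown.
4. **A covariate helps.** It might be thought that adjusting for vaccination achieves nothing against a mislabelled outcome. The simulation shows otherwise for unequal uptake. Only the attenuation remains.

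**Conclusion.** The concern holds as a risk under an unfinished event definition. The SAP lets symptoms alone make a primary event, plans to choose those symptoms without reference to vaccination, and has no COVID-19 vaccination variable, although protocol v1.1 collects the data and says they will be accounted for.

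The size depends on unknown uptake and symptom frequency. Across assumed false-event risks of 0.5% to 12%, equal in both groups, the planned 0.78 is seen as 0.79 to 0.907 and Schoenfeld power falls to between 79% and 40%. With 20% vs 40% uptake and 20% scored, an inert drug shows 0.79 or 1.26. The documents fix neither the direction nor the frequency of the bias. The stated sample-size figure itself is not in error.

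**What to change.** Update the SAP to protocol v1.1 and settle the symptom rule before outcome data are seen. Then:

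- State in SAP 3.5.1 and 6.3.9 that a symptom-only report in a survey interval in which a COVID-19 vaccine is newly reported does not count as infection, unless the same episode has a positive PCR or antigen test, a clinical diagnosis or a COVID-19 hospitalisation. The worker stays at risk.
- Add a time-varying vaccination (dose-interval) term to the primary model.
- Tabulate excluded events by prophylaxis group and rerun the primary analysis without the rule.

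The interval-based rule and the term need only the weekly vaccine item. The costs to state are:

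- Some untested true infections that start in a dose interval will be missed.
- Appendix 2 lists no dose date or dose number. A repeat dose of the same product may be missed, and a tighter window such as 3 days is usable only if dates exist.
- Follow-up intervals can exceed one week (protocol Table 1, footnote c), so an exclusion may cover more than a week of symptoms.
- For workers who completed the baseline survey before the vaccine questions went live (footnote e), an older dose may look new.
- Surveys completed before that date cannot be screened at all.
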